9.3 POPULATIONS FOR ANALYSES

A Per-Protocol analysis will be used where participants that complied with the protocol sufficiently to ensure that their data will likely represent the effects of exercise (i.e., participants who participated in at least 80% of the exercise sessions) are included in the dataset.

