- Secondary Endpoints: Patient-reported outcomes and other health-related components after 10 weeks post-randomization with AET+ and CON; Free-living physical activity and sleep quality after 10 weeks post-randomization with AET+ and CON.
- Exploratory Endpoints: Clinical outcomes, cardiorespiratory function, cognition, biomarkers, metabolomics, ultrasound-based muscle measurements, and vascular function after 10 weeks post-randomization with AET+ and CON; Collection of initial feasibility data to conduct exercise sessions remotely; Explore relationships between the physiological variables and post-study health outcome variables over time.

Abbreviated Title: Exercise and COVID-19**Version Date: 3/18/2025**

Study Population: Ninety male and female adults (18 to 80 years old) recovering from COVID-19, from the greater Washington DC metropolitan area.

Phase: N/A

Description of Sites/Facilities Single-site study (NIH Clinical Center)

Enrolling Participants:

[figure not shown]
Description of Study Intervention: Aerobic Exercise Training: Participants will perform aerobic exercise, 3 times a week for 10 weeks, with supervision by credentialed RMD staff members. Participants will be encouraged to target 30 minutes of continuous aerobic exercise. The intensity of exercise will be gradually increased from light-moderate to moderate-high as safely tolerated by the participant and guided using heart rate targets.
Education: Participants will have weekly education sessions for 10 weeks. All sessions are ~1 hour and will be conducted remotely by credentialed RMD staff members.

Participants randomized to AET+ will perform both exercise training and education during the 10 week intervention period. Participants randomized to CON will perform education only during the first 10 weeks, followed by exercise training during the second 10 weeks (crossover).

Study Duration: 36 months

Participant Duration: Up to 17 months if randomized to AET+, and up to 21 months if randomized to CON

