6 STUDY INTERVENTION

6.1 STUDY INTERVENTIONS ADMINISTRATION

6.1.1 Study Intervention Description

Participants in the AET+ arm will receive both exercise and education during the 10-week intervention period, while participants in the CON arm will receive exercise after completing 10 weeks of education.

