7 STUDY INTERVENTION DISCONTINUATION AND PARTICIPANT DISCONTINUATION/WITHDRAWAL

7.1 DISCONTINUATION OF STUDY INTERVENTION

Participants in the AET+ arm who are unable to complete at least 80% of the exercise sessions, will be withdrawn from the study. If a clinically significant finding is identified (including, but not limited to changes from baseline) after enrollment, the investigator or qualified designee will determine if any change in participant management is needed. Any new clinically relevant finding will be reported as an adverse event (AE).

Participants are free to withdraw from participation in the study intervention at any time upon request.

An investigator may discontinue or withdraw a participant from the study intervention for the following reasons:

- Disease progression which requires discontinuation of the study intervention
- If any clinical adverse event (AE), laboratory abnormality, or other medical condition or situation occurs such that continued participation in the study would not be in the best interest of the participant
- Investigator discretion
- Positive pregnancy test

- Participant unable to perform exercise training for 2 consecutive weeks

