7.2 PARTICIPANT DISCONTINUATION/WITHDRAWAL FROM THE STUDY

Prior to removal from the study, efforts will be made to have participants complete a safety visit within 14 days of the last exercise session.

Participants are free to withdraw from participation in the study at any time upon request.

An investigator may discontinue or withdraw a participant from the study for the following reasons:

- Significant study intervention non-compliance
- If the participant meets an exclusion criterion (either newly developed or not previously recognized) that precludes further study participation
- Concurrent enrollment in other interventional clinical trials
- Death
- Screen Failure

The reason for participant discontinuation or withdrawal from the study will be documented. Participants who sign the informed consent form and are randomized but do not receive the study intervention may be replaced. Participants who sign the informed consent form, and are randomized and receive the study intervention, and subsequently withdraw, or are withdrawn or discontinued from the study, will be replaced.

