9.2 SAMPLE SIZE DETERMINATION

The sample size is calculated based on the primary outcome of 6MWT distance. Based on findings from an RCT of similar exercise interventions in participants recovering from SARS (26), the mean improvement of the 6MWT distance in the AET+ group over the CON group is expected to be 56.7 meters ($20.7 \pm \text{SD}=98.6$ meters for the control group and $77.4 \pm \text{SD}=71.3$ meters for the exercise group). With a significance level of 0.05, 80% power and 1:1 randomization to two groups, a sample size of 38 in each group is adequate to detect such a difference. Sample size was determined by the Power Analysis and Sample Size (PASS) program for a two-sample t-test with unequal variance.

Our recruitment goal was therefore set at 76 participants, however, 85% of randomized participants are expected to complete at least the second study visit. Therefore, 90 participants

need to be randomized in order to achieve 76 completed participants. Recruitment will remain open until 38 participants in each of the AET+ and CON cohorts have completed at least the second study visit (i.e., 10-week time point).

It is expected that approximately 4 to 8 participants will be enrolled each month, such that target enrollment may be reached within 1.5 to 2 years.

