11 ABBREVIATIONS

6MWT	Six minute Walk Test
ABI	Ankle-Brachial Index
ACSM	American College of Sports Medicine
AE	Adverse Event
AET	Aerobic Exercise Training
AET+	Aerobic Exercise Training + Education Group
AI	Associate Investigator
ANCOVA	Analysis of Covariance
ANS	Autonomic Nervous System
APTA	American Physical Therapy Association
ARDS	Acute Respiratory Distress Syndrome
BDI-II	Beck's Depression Index-2
BMI	Body Mass Index
BTRIS	Biomedical Translational Research Information System
CAVI	Cardio-Ankle Vascular Index
CBC	Complete Blood Count
CFR	Code of Federal Regulations
CiSTAR	Clinical Informatics System for Trials and Research
CLIA	Clinical Laboratory Improvement Amendments
CMP	Clinical Monitoring Plan
CMR	Cardiovascular Magnetic Resonance
COC	Certificate of Confidentiality
CON	Control Group (Education Only)
CONSORT	Consolidated Standards of Reporting Trials
COVID-19	Coronavirus-2019
CPET	Cardiopulmonary Exercise Test
CR	Continuing Review
CRF	Case Report Form
CRISIS	CoRonavIruS Health Impact Survey
CRIS	Clinical Research Informatics System
CT	Computed Tomography
CTA	Computer Tomography Angiogram
DCC	Data Coordinating Center
DHHS	Department of Health and Human Services
DLCO	Diffusion Capacity
DSMB	Data Safety Monitoring Board
DSQ-PEM	DePaul Symptom Questionnaire – Post Exertional Malaise
DRE	Disease-Related Event
DVT	Deep Vein Thrombosis
EC	Ethics Committee
ECG	Electrocardiogram
Echo	Echocardiogram

Abbreviated Title: Exercise and COVID-19

Version Date: 3/18/2025

eCRF	Electronic Case Report Forms
EPII	Epidemic – Pandemic Impacts Inventory
EQ-5D-5L	EuroQoL 5-Dimension 5-Level
EtOH	Ethyl alcohol
FDA	Food and Drug Administration
FSS	Fatigue Severity Scale
FVC	Forced Vital Capacity
GCP	Good Clinical Practice
GFR	Glomerular Filtration Rate
GLP	Good Laboratory Practices
GWAS	Genome-Wide Association Studies
HAP	Human Activity Profile
HbA1c	Hemoglobin A1c
HIPAA	Health Insurance Portability and Accountability Act
HRPP	Human Research Protection Program
HSPU	Human Subjects Protection Unit
ICH	International Council for Harmonization
ICU	Intensive Care Unit
IDE	Investigational Device Exemption
IES-R	8.3.6.7 Impact of Events Scale – Revised
ILD	Interstitial Lung Disease
IMM	Independent Medical Monitor
IND	Investigational New Drug Application
IPAQ	International Physical Activity Questionnaire
IR	Infrared Imaging
IRB	Institutional Review Board
ISM	Independent Safety Monitor
ISO	International Organization for Standardization
ITT	Intention-To-Treat

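### The only analysis set is per-protocol, and before the primary endpoint its attendance filter can act only in the exercise arm, so the comparison is selected after randomisation and can be biased

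*Combined protocol and SAP*

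**What the plan says.** Section 9.3 is a single sentence. It states that "A Per-Protocol analysis will be used where participants that complied with the protocol sufficiently" and explains this as "participants who participated in at least 80% of the exercise sessions". No arm is named. Section 9 contains no all-randomised set, no missing-data method and no sensitivity analysis.

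Section 9.4.2 makes 6MWT distance at Study Visit 2 the primary outcome, analysed by ANCOVA with baseline 6MWT as covariate. On what CON does before that visit, the Synopsis says "Participants randomized to CON will perform education only during the first 10 weeks", and Section 6.1.1 agrees: "participants in the CON arm will receive exercise after completing 10 weeks of education". Education attendance is monitored in both arms (Section 6.3) but is not a criterion for the analysis set.

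Three further provisions bear on who reaches Visit 2:

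- Section 7.1: "Participants in the AET+ arm who are unable to complete at least 80% of the exercise sessions, will be withdrawn from the study".
- Section 7.2: people who were randomised, received the intervention "and subsequently withdraw, or are withdrawn or discontinued from the study, will be replaced". Before removal the plan seeks a safety visit; it does not mention a Visit 2 6MWT.
- Section 9.2: "Recruitment will remain open until 38 participants in each of the AET+ and CON cohorts have completed at least the second study visit".

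**The concern.** Attendance is known only after randomisation, and in this population it is unlikely to be unrelated to prognosis. The protocol accepts that post-exertional malaise can emerge during training (Sections 2.3.1.8 and 2.3.1.15) and lists illness and adverse events as reasons for stopping the intervention (Section 7.1). Such events could lower both attendance and walking distance.

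If AET+ is reduced to those who sustained training while CON is left as randomised, the arms no longer differ only by exercise, which is the basis claimed for the design in Section 4.2. Part of a positive 6MWT result could then reflect who was kept. No other set is defined, so the secondary outcomes inherit the same problem.

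The withdrawal and replacement rules take it beyond the choice of dataset. A non-attending AET+ participant may never provide a primary outcome, and someone else is recruited in their place.

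**Working it through.** **1. The plan's own figure.** Inputs from Section 9.2: difference 77.4 − 20.7 = 56.7 m; SDs 98.6 m (control) and 71.3 m (exercise); alpha 0.05, taken as two-sided; 80% power; unequal-variance t-test. Power is 79.8% at 37 per arm and 80.8% at 38, so 38 per arm reproduces. 76 / 0.85 = 89.4, so 90 to randomise also reproduces. The sample size is not in error for the test it describes.

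**2. Standard error at 38 per arm.** SE = √(98.6²/38 + 71.3²/38) = √(255.8 + 133.8) = 19.7 m.

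**3. Bias from a filter in one arm.** Let p be the share of AET+ excluded and g the gap in mean 6MWT change, attenders minus non-attenders, that would exist with no exercise effect. The whole-arm mean is (1 − p) × attenders + p × non-attenders, so the attenders' mean exceeds it by p × g. CON is unfiltered, so the comparison shifts by p × g.

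**4. Type I error.** With k = p × g / SE, the two-sided error is Φ(k − 1.96) + Φ(−k − 1.96). The documents give neither p nor g. Assuming g = 60 m:

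| AET+ excluded | Bias | k | Two-sided type I error |
|---|---|---|---|
| 5% | +3 m | 0.15 | 5.3% |
| 15% | +9 m | 0.46 | 7.4% |
| 30% | +18 m | 0.91 | 14.9% |

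At g = 0 there is no bias. If g is negative, the bias favours CON. For scale, Section 3 sets the minimal important difference at 30 m.

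**5. Cross-check with another model.** Suppose attendance follows a latent normal variable with correlation r to 6MWT change, SD 71.3 m, and the lowest share is removed from AET+ only. The shift is r × 71.3 × φ(z)/(1 − p), where z is the normal quantile at p. Two-sided rejection rates are simulated with no true effect and 38 per arm.

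| AET+ excluded | Shift, r = 0.3 | Rejection | Shift, r = 0.5 | Rejection |
|---|---|---|---|---|
| 5% | +2.3 m | 5.0% | +3.9 m | 5.6% |
| 15% | +5.9 m | 6.0% | +9.8 m | 7.9% |
| 30% | +10.6 m | 8.2% | +17.7 m | 14.7% |

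At r = 0 the shift is nil. At r = −0.3 with 15% excluded it is about −6 m. A 60 m gap therefore corresponds to r of about 0.5, towards the upper end of these assumptions.

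**6. Power for an all-randomised analysis.** Assume 15% of AET+ gain nothing: 56.7 × 0.85 = 48.2 m. Keep the SDs above. For ANCOVA, multiply the change-score variance by (1 + ρ)/2, where ρ is the baseline/follow-up correlation (equal variances assumed): 0.75 at ρ = 0.5 and 0.90 at ρ = 0.8.

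| Observed per arm | t-test | ANCOVA, ρ = 0.5 | ANCOVA, ρ = 0.8 |
|---|---|---|---|
| 38 | 67% | 79% | 72% |
| 45 (all 90) | 75% | 86% | 79% |

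Allowing the AET+ SD to widen because some gain and some do not lowers the t-test figures by about one point, to 66% and 74%.

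**The case against.** The best defence is that few people will be excluded. Section 2.2 reports attendance above 85% and full completion in the SARS trial used for sizing. Section 4.3 reports high adherence in the team's similar programmes. AET+ sessions are directly supervised with make-up sessions allowed (Section 6.1.1.2), and people with post-exertional malaise at screening are not enrolled. The 85% completion in Section 9.2 covers both arms and all causes; it is not an AET+ non-attendance rate. This stands: the 5% row deserves as much weight as the 15% row, and the 30% row has no support in the documents.

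It can also be said that the planned ANCOVA might absorb some of the selection. It can do so only for what is measured at baseline. Intolerance that emerges during training is not.

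A third argument is that the investigators want the effect in people who train. Comparing selected attenders with unselected controls does not estimate that without further assumptions.

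Two stronger readings are tempting. A reader might infer that Section 9.3 empties the CON arm, since nobody in CON has exercise sessions before Visit 2. Sections 9.2 and 9.4.2 plainly require a CON group at Visit 2, so that is not the intended meaning. Applying the filter to CON's crossover sessions would not help, because it would select CON on behaviour after the endpoint was measured. A reader might also take "Intention-To-Treat" in the abbreviation list (Section 11) as the trace of a dropped analysis. The list carries other terms the plan never uses, so this shows nothing.

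**Conclusion.** The structural fault is established from the text and depends on no assumed number. There is one analysis set, its criterion can operate only in AET+ before the primary endpoint, and the withdrawal, replacement and recruitment rules act in the same direction. As written, the primary and secondary comparisons are not comparisons of the groups as randomised, and this must be changed.

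A reader might go further and conclude that the result will be tilted towards exercise by a material amount. The documents do not support that. The direction is a reasonable inference, resting on poor attenders having smaller 6MWT gains for reasons unrelated to exercise. The size is unknown. Under the assumed 60 m gap, which is larger than the plan's whole expected effect, the bias runs from 3 m at 5% excluded to 18 m at 30%, with type I error from about 5.3% to 15%. It is zero if there is no gap and reverses if the gap does.

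**What to change.** **Analysis set.** Rewrite Section 9.3 so that the primary set is all randomised participants, analysed as randomised, using the planned baseline-adjusted ANCOVA. Use the same set for the secondary endpoints. Keep the 80% set as supportive only.

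**Data collection.** Rewriting Section 9.3 alone will not work. If Sections 7.1, 7.2 and 9.2 stand, non-attenders may have no Visit 2 6MWT, and imputation would extrapolate beyond anyone observed. These sections must be reconciled with the new set so that stopping training does not end outcome collection, the Visit 2 6MWT is sought from everyone regardless of attendance, and participants who have been replaced stay in the analysis. When a participant stops training remains a clinical matter that this change does not touch.

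**Missing data.** Specify multiple imputation for missing Visit 2 values, using arm, baseline 6MWT, sessions attended and reason for stopping, with a delta-adjusted sensitivity analysis for AET+.

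**Optional.** A complier estimate with randomisation as the instrument may be added. It must state its exclusion restriction, which is doubtful with an 80% cut because partial attenders may benefit.

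**Cost.** Protocol and SAP wording, follow-up of people who stop training, and possible dilution. On the 15% assumption, power should be restated from the table in the working: 67% by t-test with 38 per arm observed, up to 86% by ANCOVA with all 90 observed and a correlation of 0.5. The 56.7 m comes from a trial whose own attendance was incomplete, so some dilution may already be counted.

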9.4 STATISTICAL ANALYSES

9.4.1 General Approach

For descriptive statistics, continuous data will be presented as means with standard deviation and categorical data as percentages. The study will be powered under the assumption that no informative covariates are identified and using 6MWT as the primary outcome. We will include the baseline outcome measure in the model (i.e., the value of the dependent variable at baseline). Assumptions for normality will be assessed as appropriate.

9.4.2 Analysis of the Primary Endpoints

The primary endpoint for this study is physical function, as measured by 6MWT distance after 10 weeks post-randomization. An analysis of covariance (ANCOVA) will be used for objective #1, with the 6MWT distance after the 10-week intervention (study visit 2) as the dependent variable, baseline 6MWT distance (study visit 1) as the covariate and treatment group as the fixed factor. Other factors related to participant characteristics such as timing (e.g., early vs. late study entry) and those related to COVID-19 severity (e.g., age, comorbidities, hospital admission, duration of hospitalization, ventilator use, drug treatments, etc.) may have potential effects on the primary outcome and may be included as covariates in the model. The association between these baseline (i.e., pre-randomization) patient characteristics and the primary outcome will be tested in bivariate and multivariable analyses, and the optimal set of predictors will be included in the final model to account for baseline participant characteristics that may affect recovery.

9.4.3 Analysis of the Secondary Endpoints

A secondary endpoint for this study is the patient-reported outcomes and other health-related components, as well as free living physical activity and sleep quality. An analysis of covariance (ANCOVA) will be used for objective #2 and #3, with the variables of interest after the 10-week intervention (study visit 2) as the dependent variable, baseline variables (study visit 1) as the covariate and treatment group as the fixed factor. Other factors related to participant characteristics such as timing (e.g., early vs. late study entry) and those related to COVID-19 severity (e.g., age, comorbidities, hospital admission, duration of hospitalization, ventilator use, drug treatments, etc.) may have potential effects on secondary outcomes and may be included as covariates in the model. The association between these baseline (i.e., pre-randomization) patient characteristics and secondary outcomes will be tested in bivariate and multivariable analyses,

and the optimal set of predictors will be included in the final model to account for baseline participant characteristics that may affect recovery.

Analyses of secondary endpoints are not dependent on findings of the primary endpoints.

9.4.4 Safety Analyses

Not Applicable

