To minimize risk and maximize safety, participants will be evaluated by NIH cardiology, perform medical history and physical examination, ECG, Doppler cardiac echocardiography, and pulmonary function tests with DLCO, to exclude those with contraindications to exercise prior to the CPET. During the CPET, participants will be monitored by continuous 12-lead ECG. Prior to beginning the test, participants will be informed of the signs and symptoms of heart disease and questioned frequently during the test regarding their presence. As recommended by the American Heart Association and the American College of Sports Medicine (ACSM), exercise will be overseen by personnel appropriately trained in clinical exercise testing ([49](#)). In addition, a licensed independent practitioner (LIP) will be present during all exercise tests. The investigators and clinical exercise training and testing staff in our laboratory are highly experienced in cardiopulmonary exercise testing, even in high-risk patients such as those with pulmonary artery hypertension and interstitial lung disease. As PEM may develop even among those reporting no PEM on enrollment, the presence of significant symptoms consistent with PEM may be captured during the qualitative interviews. These interviews were specifically developed to detect the presence of PEM and are performed by LIPs and/or persons with experience and skill conducting interviews for identifying the presence of PEM. The impact of exercise on post COVID-19 condition and PEM is still unresolved, therefore the clinical team will monitor for possible development of PEM symptoms throughout the study and manage participants accordingly.

Risk of injury also includes those related to falling on a moving treadmill belt, such as abrasions, contusions, cuts, sprains, and fractures. The likelihood that any of these injuries would occur is small and preventive measures will be enforced to ensure that the risks remain at a minimum.

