- Perform qualitative interviews before, during and after the CPET to monitor the development of significant symptoms consistent with PEM. Interviews are performed by LIPs and/or persons with experience and skill conducting interviews for identifying the presence of PEM.

- Gradual exercise progression with supervision by RMD staff members specifically credentialed for the supervision of aerobic exercise in clinical populations
- Assess and monitor symptoms and tolerance of previous exercise sessions by RMD staff members to adjust exercise sessions as necessary.

In general, health risks during exercise are very small. These risks are considered to be even smaller when maximal exercise evaluations are performed under supervised and safe clinical conditions, and additional medical tests and examinations related to defining the seriousness of the patients' conditions are performed. Improvement in cardiorespiratory fitness enables individuals to accomplish a given amount of activity or work at a lower percentage of their peak capacity and with less fatigue. Moreover, improvement of exercise tolerance generally increases quality of life by permitting individuals to engage more easily in daily physical activities. Specifically as it pertains to COVID-19, "...there is a strong rationale for incorporation of exercise prescription in management of Long COVID based on cardiac deconditioning as a major contributor to symptom burden and the well-described physiologic responses (and benefits) of exercise on the cardiovascular system"([56](#)). Early reviews of the available literature on exercise training post-COVID suggest improved physical functioning and quality of life among non-hospitalized ([55](#)) and hospitalized ([57](#)) individuals. It is anticipated that the potential benefits of participating in an aerobic exercise conditioning program outweighs the minimal risks associated with exercise in patients recovering from COVID-19. Thus, this protocol involves greater than minimal risk to study participants, with the prospect of direct benefit to individual participants.

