3 OBJECTIVES AND ENDPOINTS

OBJECTIVES	ENDPOINTS	JUSTIFICATION FOR ENDPOINTS
Primary		
#1. To examine the effect of aerobic exercise training (AET) on physical function in participants recovering from COVID-19	Physical function is represented by the distance walked (in meters) during a 6 minute walk test (6MWT) as the primary outcome. Other measures of physical function include the time to exhaustion on the CPET and the SPPB/Mini-BEST score. All physical function outcomes will be measured at baseline and after the AET and CON regimens, and after crossover in the CON group.	The 6MWT distance has been used to reflect longitudinal changes in physical function among patients with ARDS (17 , 58) and SARS (18 , 59), and to detect changes due to exercise participation in patients recovering from SARS (26). In the only study found to date that utilized a training intervention in patients with COVID-19, the 6MWT was used in the RCT to examine changes in exercise capacity following 6 weeks of respiratory training (60).

OBJECTIVES	ENDPOINTS	JUSTIFICATION FOR ENDPOINTS
		A minimal important difference (MID) has yet to be established among survivors of COVID-19. We will consider 30 meters as the MID for this study based on reported ranges of 20 to 30 meters in patients with idiopathic pulmonary fibrosis (61 , 62) and ARDS (63).
Secondary		
#2. To examine the effect of AET on patient reported outcomes and other health-related quality of life (QoL) components in participants recovering from COVID-19	Patient reported outcomes related to fatigue, sleep, post-exertional malaise, post-traumatic stress disorder, depression, anxiety, general and COVID-19 specific QOL outcomes. These outcomes are measured at baseline and after the AET and CON regimens, after crossover in the CON group, and every 3 months for 1 year.	There are currently no studies available regarding the effect of exercise on these outcomes on recovery from COVID-19. It is expected that QOL will be improved with AET as aerobic exercise has been associated with improvements in patient-reported outcomes and health-related QOL in the lung disease population (64-66).

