4 STUDY DESIGN

4.1 OVERALL DESIGN

This is a single-site randomized controlled trial with a wait-list (cross-over) design. The study will be led by the Rehabilitation Medicine Department (RMD) at the NIH Clinical Center, in collaboration with other NIH institutes. An overview of the study is as follows:

The overall aim of this RCT is to determine whether AET is beneficial for improving functional outcomes and recovery among survivors of COVID-19. All participants will perform baseline assessments (Study visit 1) including physical, cognitive testing, patient-reported outcomes, and vascular function as listed in **Section 8, Study Assessments and Procedures**. Thereafter, participants will be randomized to either one of 2 arms for 10 weeks: 1) an aerobic exercise training with education (AET+) group, or 2) a wait-list control group (CON) provided with education only. After 10 weeks, both groups will repeat the same assessments as performed at baseline (Study Visit 2; 10-week follow-up). Following this visit, participants in the CON group will crossover and perform 10 weeks of AET either on-site or remotely, followed by a third assessment visit (Study Visit #3; 20-week follow-up). Participants will also begin wearing a wristwatch accelerometer at the baseline study visit and through to the follow-up time point (10 weeks for AET+, 20 weeks for CON), for continuous collection of free-living physical activity and sleep quality. In addition, all participants will be monitored periodically over one year to capture physical activity, sleep quality and health-related QOL outcomes over time.

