8.4.4 Time Period and Frequency for Event Assessment and Follow-Up

The occurrence of an adverse event (AE) or serious adverse event (SAE) may come to the attention of study personnel during study visits and interviews of a study participant presenting for medical care, or upon review by a study monitor.

All AEs including local and systemic reactions not meeting the criteria for SAEs will be captured on the appropriate case report form (CRF). Information to be collected includes event description, time of onset, clinician's assessment of severity, relationship to study intervention (assessed only by those with the training and authority to make a diagnosis), and time of resolution/stabilization of the event. All AEs occurring while on study must be documented appropriately regardless of relationship. All AEs will be followed to adequate resolution.

Any medical condition that is present at the time that the participant is screened will be considered as baseline and not reported as an AE. However, if the study participant's condition deteriorates at any time during the study, it will be recorded as an AE.

Changes in the severity of an AE will be documented to allow an assessment of the duration of the event at each level of severity to be performed. AEs characterized as intermittent require documentation of onset and duration of each episode.

Clinical research staff will record all reportable events with start dates occurring any time after informed consent is obtained until 7 (for non-serious AEs) or 14 days (for SAEs) after the last day of study participation. At each study visit, the investigator will inquire about the occurrence of AE/SAEs since the last visit. Events will be followed for outcome information until resolution or stabilization.

All serious adverse events (SAEs) will be followed until satisfactory resolution or until the PI deems the event to be chronic or the participant is stable.

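### No adverse-event summary by arm is planned for the only period with a non-exercise control

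*Combined protocol and SAP*

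**What the plan says.** Section 9.4.4 reads, in full, "Not Applicable". Section 2.3.3 concludes that "this protocol involves greater than minimal risk to study participants", and Section 2.3.1.8 says "The impact of exercise on post COVID-19 condition and PEM is still unresolved".

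Safety data are collected throughout. Section 8.4.4 states "All AEs occurring while on study must be documented appropriately regardless of relationship" and "At each study visit, the investigator will inquire about the occurrence of AE/SAEs since the last visit". It lists severity, relationship to the intervention, onset and resolution among the items recorded. The Schedule of Activities has AE review in both arms.

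On design, Section 4.1 says of Study Visit 2: "Following this visit, participants in the CON group will crossover and perform 10 weeks of AET either on-site or remotely".

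Section 9.3 defines one analysis set, per-protocol, limited to people who attended at least 80% of exercise sessions. Section 7.1 withdraws AET+ participants below that level, and Section 7.2 replaces treated participants who withdraw. Safety appears elsewhere in Section 9 only in Section 9.4.9, under the feasibility objective for the control (CON) group after crossover.

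PEM is handled as an efficacy-type outcome. The secondary endpoints in Section 3 are "Patient reported outcomes related to fatigue, sleep, post-exertional malaise, post-traumatic stress disorder, depression, anxiety, general and COVID-19 specific QOL outcomes". Section 8.3.6.6 names the VAS-CFS as the instrument for PEM, and Section 9.4.3 compares secondary outcomes between arms by ANCOVA at Visit 2.

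**The concern.** The trial asks whether aerobic training benefits people recovering from COVID-19, and it treats the effect of exercise on PEM as an open question. A reader of the results will want the benefit and the harm side by side, against the same control. The plan supplies an estimate of the 6MWT difference among people who attended, and no specified estimate of AE frequency by arm.

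Two things follow from leaving the section empty. The population is open: if safety defaults to the one set defined in Section 9.3, those who stopped because exercise harmed them can drop out of the count. The period is also open: after Visit 2 the control arm exercises too, so a total by arm over the whole study would no longer contrast exercise with no exercise.

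**Working it through.** **1. The plan's own size.** Section 9.2 gives a difference of 56.7 m, SDs of 98.6 and 71.3 m, significance level 0.05 and 80% power, using a two-sample t-test with unequal variances. The standard error at n per arm is √((98.6² + 71.3²)/n). At n = 38 this is √(14,805.65/38) = 19.74 m, so the noncentrality is 56.7/19.74 = 2.87. With Welch degrees of freedom and a two-sided test, power is 80.8% at 38 and 79.8% at 37, so 38 per arm reproduces. Allowing for 85% completion, 76/0.85 = 89.4, which rounds up to 90, or 45 per arm. This part of the plan is sound and fixes the precision available for safety.

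**2. Which period is controlled.** CON begins training after Visit 2 (Section 4.1). In the Schedule of Activities, AE review runs to Week 69 in AET+ and Week 84 in CON. That is 84 − 69 = 15 weeks longer in CON, and 15/69 = 22%. The extra time includes CON's own 10 weeks of exercise. Only the period from randomisation to Visit 2 compares exercise with no exercise.

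**3. What the attendance rule can do.** The threshold is 0.80 × 30 = 24 sessions. Before Visit 2 only AET+ has exercise sessions, so in the controlled period the rule removes people from that arm. Let p be the true share of AET+ with a given harm, and f the share of those affected who fall below 24 sessions. If nobody else is excluded, the rate seen in the per-protocol set is p(1 − f)/(1 − pf). The documents give no event rates, so p = 20% is an assumption:

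| f | Rate seen |
|---|---|
| 0% | 20.0% |
| 25% | 15.8% |
| 50% | 11.1% |
| 75% | 5.9% |
| 100% | 0% |

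**4. What the planned PEM comparison covers.** The VAS-CFS has 12 items and is given up to seven times around each CPET (Section 8.3.6.6). Section 9.4.3 does not say which items or times enter the ANCOVA. The comparison is of mean scores after a maximal test that both arms perform, in the per-protocol set. It does not measure PEM during training or count affected people.

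**5. Precision of a by-arm table.** With zero events among n, the exact two-sided 95% upper limit is 1 − 0.025^(1/n).
- n = 45: 7.9%
- n = 38: 9.3%

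This bound suits rare events such as SAEs. It does not suit any AE, since Section 2.3.1.15 expects soreness and fatigue. For commoner events, assume 10% in CON and 20% in AET+. The approximate 95% half-width of the risk difference is 1.96 × √((0.10 × 0.90 + 0.20 × 0.80)/n), which is 14.6 percentage points at 45 and 15.9 at 38. Fisher exact power for an assumed 5% against 20% is 48% at 45 per arm and 38% at 38.

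**The case against.** The strongest reply is that harm is not ignored. AEs are documented in both arms, an independent medical monitor is told of significant events and can see the data (Section 10.5), events go to the IRB (Section 8.4.5), and individual data are listed (Section 9.4.8). Deterioration in fatigue, mood, quality of life or lung function would also appear in the planned Visit 2 comparisons. All of this is true. But oversight and listings set no population, period or by-arm estimate, and the Visit 2 comparisons share the attendance restriction.

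Four stronger readings are tempting, and the documents do not support them:
- **That the trial cannot compare harm between arms.** The AE data will exist in both arms. What is missing is the specified analysis.
- **That PEM goes uncompared.** Sections 3, 8.3.6.6 and 9.4.3 together plan a between-arm comparison at Visit 2, with the limits described above.
- **That a misleading whole-study count is planned.** No section plans one. The Week 84 against Week 69 difference only shows why the period must be fixed.
- **That AE reporting is confined to the per-protocol set.** Section 9.3 does not say so. It simply offers no other set.

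Two practical objections also stand. A yes/no PEM endpoint built from the VAS-CFS or the interviews has no threshold in the documents. Follow-up to Visit 2 will also be incomplete, because Section 7.2 promises only efforts at a safety visit for people leaving the study.

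**Conclusion.** The point holds as an omission in the analysis plan, and it should be corrected. Section 9.4.4 rules out safety analysis in a trial that rates itself above minimal risk and collects the data needed. No by-arm AE summary is planned for the controlled period. Safety is named only for an uncontrolled phase, and the sole analysis set can lose people who stopped because of harm.

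The size of any resulting distortion cannot be stated, because the documents give no AE or PEM rates; the table in the working is an illustration under an assumed 20%. The precision limits of 7.9% and 9.3% assume 45 or 38 people in an arm with no events. Forty-five is an expectation, since withdrawn participants are replaced and recruitment continues until 38 per arm complete Visit 2. At these numbers only large differences would be detectable, so the tables should be descriptive.

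**What to change.** Replace the entry in Section 9.4.4 with the following.

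- **Population and period:** all randomised participants, by assigned arm, from randomisation to Study Visit 2, or to last contact for those withdrawn sooner.
- **Content:** number and share with any AE, any SAE, any related AE, any AE leading to stopping the intervention or to withdrawal, and PEM recorded as an AE. Give risk differences with exact or score 95% intervals.
- **PEM scores:** run the Visit 2 VAS-CFS comparison also in all randomised participants with data, and state in advance which items and time points are used.
- **Crossover:** report CON events during its exercise phase in a separate table labelled uncontrolled. Do not compare whole-study totals between arms.
- **Caveats to print with the tables:** AET+ has more occasions on which an AE can be noticed (three exercise check-ins a week, Section 2.3.3, on top of the weekly remote education that is CON's only regular contact, Section 6.1.1.1). Follow-up after withdrawal is incomplete (Sections 7.1 and 7.2). Precision is low.

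For recorded AEs this costs a few tables, with no new procedures and no change to the 38 per arm or the 90 randomised. The VAS-CFS analysis is a rerun on existing data. The PEM count will be only as complete as its recording as an AE, and the text should say so.
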